5.1 Study Intervention Phase

The following procedures will be carried out on each study visit. See section 5.1.7 for a detailed description of each procedure.

5.1.1 Lab Visit 1

Consent

Motor threshold testing

White noise habituation

Shock workup

NPU

Sternberg working memory task

5.1.2 MRI visit

Basic MRI scans

5.1.3 TMS visits (1-4)

Either cTBS or iTBS

5.1.4 Lab Visit 2

White noise habituation

Shock workup

NPU

Sternberg working memory task

5.1.5 TMS visits (5-8)

Either cTBS or iTBS

5.1.6 Lab Visit 3

White noise habituation

Shock workup

NPU

Sternberg working memory task

CONFIDENTIAL

5.1.7 Optional MRI visit

NPU TMS/fMRI

5.1.8 Optional Pilot visits

NPU (1 run)

cTBS

NPU (1 run)

5.1.9 Procedures

TMS motor threshold testing: The resting motor threshold (MT) will be determined in order to find the safe TMS dosing level. MT is defined as the minimum magnetic flux needed to elicit a threshold EMG response in a target muscle in 5 out of 10 trials. MT is the standard in the field for measuring cortical excitability and to reduce seizure risk. MEPs for the contralateral first dorsal interosseus (FDI) muscle will be measured with EMG. The scalp region producing the largest amplitude MEP will be identified. At that scalp location, the lowest TMS intensity able to elicit 5 MEP's of $\geq 50\mu\text{V}$ in peak-to-peak amplitude in 10 trials at this site will be determined using a descending method of limits procedure.

Sternberg working memory task: On each WM trial, subjects will see a series of 4 letters presented singularly (encoding period) that will be followed by a brief interval where subjects are required to maintain these letters (maintenance period). At the end of the maintenance period, subjects will be prompted to make a response based on the task instructions (response period; Sternberg, 1966). The response prompt will consist of a letter and a number. The letter will be chosen from the study series, and the number will correspond to a position in the series. The subjects will indicate whether the position of the letter in the series matches the number.

There will be 2, 14 min runs of the experiment. Within each run, there will be 4 blocks (2 threat, 2 safe). Within each block, there will be 2 types of trials based on the delivery of startle probes. On each trial a startle probe will be presented either during the maintenance period or the ITI. There will be 6 trials per condition per block. There will be a total of 3 shocks per run presented at random points during the threat blocks.

NPU Task: The instructed fear paradigm that will be implemented uses administration of predictable and unpredictable shocks to generate phasic and sustained forms of potentiated startle. We will use the NPU threat procedure as described in (Schmitz & Grillon, 2012). The experiment consists of three different conditions: no shock (N), predictable shock (P), and unpredictable shock (U), each lasting approximately 150 sec. In the N condition, no shocks will be delivered. In the P condition, shocks will be administered predictably, that is, only in the presence of a threat cue. In the U condition, the shocks will be unpredictable. In each 150-sec condition, an 8-sec cue will be presented four times. The cues will be different geometric colored shapes in each

CONFIDENTIAL

condition (e.g., a blue square for N, a red circle for P, and a green star for U) presented on a computer monitor in front of the subjects. The cue will signal the possibility of receiving a shock only in the P condition. It has no signal value in the N and U conditions. Instructions will also be displayed on a computer monitor to inform subjects of the nature of current condition by showing the following information throughout the testing procedure: “no shock” (N), “shock only during shape” (P), or “shock at any time” (U). During each predictable and unpredictable condition, one shock will be administered during the cue in the predictable condition and in the absence of a cue in the unpredictable condition.

There will be 2, 12 min runs during each test visit. Within each run, there will be 8 blocks (2 predictable, 2 unpredictable, 4 neutral). There are twice the number of neutral blocks to ensure that safe blocks alternate with threat (predictable or unpredictable) blocks. Startle probes will be presented either during the cue period, or the ITI. During the predictable and unpredictable blocks, there will be 2 trials per condition. Given that there will be twice as many neutral blocks, during these blocks there will only be 1 trial per condition. There will be a total of 3 shocks per run presented during either the ITI (unpredictable) or cue (predictable) periods.

White noise habituation: The acoustic startle stimuli will be a 40-ms burst of white noise (103 dB) with instantaneous rise time. Auditory stimuli will be delivered binaurally via headphones. The eyeblink component of the startle response will be measured by recording electromyographic (EMG) activity of the left orbicularis oculi muscle. The session will begin with a startle habituation phase with 9 startle stimuli presented alone to reduce startle reactivity.

Shock workup: Electric shocks will be delivered through two tin disk electrodes located on the median nerve of the right wrist with a current constant stimulator. During each test visit prior to the experiment, the subject will undergo a shock workup procedure to identify an appropriate shock level. During the workup, subjects will receive brief (100 ms) presentations of the shock starting at a low level (2 mA), which will be increased in intensity gradually, until it reaches a level that they rate as uncomfortable but tolerable. Shocks will be administered at that level during the visit. The subject will also be informed that they are free to withdraw from the experiment if they later determine that the shock level is too high.

Self-report Questionnaires: Subjects will be asked to fill out self-report questionnaires during the experiments (i.e. TMS adult safety screen (Keel, Smith, & Wassermann, 2000), the State Anxiety Scale (S-Anxiety)(Spielberger, 1987), the Beck Anxiety Inventory (Beck, Epstein, Brown, & Steer, 1988), Retrospective Threat Questionnaire). During the test visits, subjects will be asked to retrospectively rate their fear and anxiety levels using an analog scale during each condition (Retrospective Threat Questionnaire). Retrospective measures of fear and anxiety will be collected on an analog scale ranging from 0 (not at all anxious) to 10 (extremely anxious). This analog scale has been a reliable measure of anxiety in our past studies. The State Anxiety Scale (S-Anxiety) (Spielberger, 1987) a 20-item self-administered rating scale with measures of mood.

CONFIDENTIAL

cTBS: Subjects will receive a continuous train of triplet 50 Hz bursts, repeated at 5 Hz. They will receive a total of 600 pulses per session. Consistent with the iTBS condition, TMS will occur during the Sternberg WM paradigm.

iTBS. Subjects will receive 20 trains of triplet 50 Hz bursts, repeated at 5 Hz; 2 s on and 8 s off for a total of 600 pulses per session and a total duration of 3 min. and 9 s). Stimulation will occur while subjects are doing the Sternberg WM paradigm, which should facilitate the efficacy of the stimulation by taking advantage of the cognitive paired-associate stimulation (C-PAS) principle (Luber et al., 2017). The timing of the Sternberg task will be jittered so that each rTMS train will be administered during the maintenance interval of a WM trial.

Basic scans: During the MRI visit, we will collect at T1, a T2, and a diffusion-weighted echo-planar image using an available 3T scanner. Next subjects will undergo a two runs of the Sternberg task, without shocks, probes, or TMS pulses to serve as functional localizers to identify a dIPFC. Subjects may also undergo a resting state scan.

NPU TMS/fMRI. A Magventure MagPro 100X stimulator with a MRi-B91 figure-8 coil will be used. The TMS coil will be placed on the head over the target. TMS intensity will be 100% of the motor threshold (MT). For sham stimulation, a 4 cm spacer will be placed between the subject's scalp and the TMS coil. As with the study visits, subjects will have Neutral, Predictable, and Unpredictable periods. During the neutral periods, they will be safe from shocks. During the predictable periods, they can receive shocks but only when there is a cue present. During the unpredictable periods, they will be at risk for shock during the entire duration of the block. Rather than probing their ongoing fear and anxiety with the startle probes, we will replace the startle probes with single TMS pulses to the right dIPFC. This will allow us to causally examine the effect of right dIPFC activity (induced by the TMS pulse) on the neural activity that mediates fear (during the predictable cue) and anxiety (during the unpredictable cue and ITI). Importantly, by replacing the startle probes with TMS pulses, it will be possible to directly compare the TMS-evoked BOLD responses to the pattern of startle responses collected during the MRI/pre-stimulation visit. Subjects will have 1 run of active stimulation and one run of sham stimulation. Subjects may receive an additional 1 run of active stimulation at a control site in over the parietal cortex.

5.2 Subject Withdrawal

Subjects will be informed that they can withdraw from the study whenever they wish. Sample shocks will be administered prior to the study. At this point, subjects will be explicitly asked if they wish to continue. The experiment will also be stopped for any subject who exhibits signs of distress during any phase of the study. The subject will be withdrawn at any time if unable to follow the rules for participation in this study.

5.3 Early Termination Visits

CONFIDENTIAL

If a subject is withdrawn from the study or decides to discontinue, they will be compensated for the visits they completed, and a note will be placed in their CRF.

6 Statistical Plan

6.1 Primary Endpoints

Aim 1: Determine the effect of a 1-week course of TBS treatment (Continuous vs. Intermittent; right dlPFC target) on anxiety using the Neutral, Predictable, and Unpredictable (NPU) shock-threat paradigm.

Outcome measures. Fear potentiated startle (FPS) will be calculated by subtracting the blink magnitude during the predictable inter-trial interval (ITI) from the predictable cue. Anxiety potentiated startle (APS) will be calculated by subtracting the blink magnitude during the neutral ITI from the unpredictable ITI. Online anxiety ratings will be processed similarly.

Statistical Analysis. The main analysis will be a 3 [stimulation: pre-stimulation vs. post-active vs. post-sham] by 2 [protocol: cTBS vs. iTBS] repeated-measures ANOVA. In addition to the main factors considered, we may also co-vary out several individual difference measures (e.g. baseline anxiety via self-report questionnaires, counterbalance order, overall stimulation accuracy, and Sternberg working memory (WM) performance to assess target engagement).

Aim 2: Determine the effect of a 1-week course of TBS treatment (Continuous vs. Intermittent; right dlPFC target) on anxiety-related WM-deficits using the Sternberg WM paradigm during threat of shock.

Outcome measures. During each Sternberg trial, subjects will see a series of 5 or 8 letters presented singularly (encoding period) that will be followed by a brief interval where subjects are required to maintain these letters (maintenance period). At the end of the maintenance period, subjects will indicate whether the position of the letter in the series matches the number. Accuracy will be scored as the percent correct for each trial type.

Statistical Analysis. The main analysis will be a 3 [stimulation: pre-stimulation vs. post-active vs. post-sham] by 2 [protocol: cTBS vs. iTBS] repeated-measures ANOVA. As with Aim 1, we may also include several other individual difference measures as covariates in this analysis.

Aim 3: Demonstrate target engagement by measuring BOLD responses evoked by TMS pulses to the right dlPFC during threat of shock.

Outcome measures. Standard Multi-echo fMRI preprocessing will be conducted using the AFNI software package. Steps include: slice-time correction, despiking, volume registration, TE-dependent ICA denoising (to remove non-BOLD artifacts), masking, blurring, scaling, motion scrubbing, T1-EPI alignment, normalization (using MNI template). At the first level, variable duration mini-blocks will be used to model BOLD activity during the maintenance interval of the Sternberg trials. Motion parameters and all other events will be included in the model as regressors of no interest.

Statistical Analysis. Whole-brain maps will be created for contrasts mirroring those used to create FPS and APS in Aim 1. FP-BOLD and AP-BOLD maps will then be analyzed using a paired-sample t-test to compare BOLD responses evoked by active TMS and those evoked sham scalp stimulation. Monte Carlo simulations will be conducted to cluster-correct the results using a voxelwise p-value threshold of 0.001, a cluster alpha of 0.05, and a realistic spatial autocorrelation function to model the noise. This is the standard approach implemented in AFNI following the influential Eklund et al. 2016 paper. As with Aim 1, we may also include several other individual difference measures as covariates in this analysis.

CONFIDENTIAL

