This research is significant because upon completion, we expect to have direct evidence for a causal role of the right dIPFC in anxiety regulation, complete with evidence

CONFIDENTIAL

of target engagement through simultaneous TMS/fMRI, and a novel application to anxiety. This research will lay the groundwork for my long-term career objective, which is to develop an independent, NIH-funded research program employing psychophysiology, neuroimaging, and neuromodulation in healthy and anxious participants aimed at developing a circuit-level understanding of the neurobiological mechanisms underlying anxiety.

2 Study Objectives

Aim 1: Determine the effect of a 1-week course of TBS treatment (Continuous vs. Intermittent; right dlPFC target) on anxiety using the unpredictable shock-threat paradigm. Our hypothesis, consistent with our pilot data, is that strengthening circuits in the right dlPFC will facilitate anxiety regulation. Accordingly, we expect excitatory but not inhibitory TBS (compared to sham) to reduce induced anxiety.

Aim 2: Determine the effect of a 1-week course of TBS treatment (Continuous vs. Intermittent; right dlPFC target) on anxiety-related WM-deficits using the Sternberg WM paradigm during threat of shock. Our hypothesis is that the rTMS will strengthen right dlPFC circuits, which will rescue the anxiety-related WM deficits. Accordingly, we expect that 10 Hz rTMS (compared to sham) will improve accuracy on the Sternberg WM task during threat.

Aim 3: Demonstrate target engagement by measuring BOLD responses evoked by TMS pulses to the right dlPFC during threat of shock. Our hypothesis is that direct stimulation of the right dlPFC will reduce ongoing anxiety-related activity. Accordingly, we expect active but not sham TMS pulses to the right dlPFC to evoke BOLD deactivations in regions of the fear/anxiety network (i.e. amygdala, BNST, anterior insula).

3 Investigational Plan

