3.1 General Design

Aims 1 and 2 of this project will be tested using a between-subjects design where 1 group of healthy volunteers will receive 4-day courses of active and sham cTBS stimulation to the right dlPFC, while the other group will receive 4-day courses of active and sham iTBS stimulation to the right dlPFC. In Aim 1, we will test the effects of this stimulation on anxiety during the NPU threat task. In Aim 2, we will test the effects of this stimulation on anxiety-related WM deficits using the Sternberg WM paradigm. In addition, we will also administer several self-report questionnaires to assess their baseline (pre-stimulation) anxiety. Subjects will be randomly assigned to groups, and the order of stimulation (active vs. sham) will be counterbalanced across subjects. Aim 3 will be tested using a within-subjects design where this same group of subjects will receive single-pulse active and sham stimulation to the right dlPFC during the NPU threat task while in the MRI scanner. BOLD activity to the TMS pulses will be the primary outcome measure.

Subjects will undergo 12 study visits spaced over a 4-week period (Figure 3). Subjects may also be offered an optional 13th visit where TMS/fMRI is conducted. On Week 1,

CONFIDENTIAL

subjects will undergo a pre-stimulation behavioral visit where they complete the NPU threat task and the Sternberg WM paradigm, and a pre-stimulation MRI visit where they undergo all the structural and functional imaging needed to identify the optimal target of stimulation for the course of TMS used in Aims 1 and 2. This information will be used to perform neuronavigation during the study visits to ensure accurate target stimulation. Subjects will complete the TMS/fMRI scans needed for Aim 3 during the optional visit. On Weeks 2 and 4, subjects will undergo 5 visits. The first 4 visits will be stimulation visits where they receive either active or sham stimulation while doing the Sternberg WM task. On the 5th visit, they will return for the post-stimulation test visit, where they will complete the NPU threat task and the Sternberg WM paradigm.

[figure not shown]

Figure 3: Timeline showing subject visits in the proposed project.

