4.5 Total Number of Subjects and Sites

The target number of completers will be N=56. We anticipate that about 20% of subjects (N=11) will terminate the study during the task because of discomfort and another 10% (N = 5) to withdraw due to scheduling issues. An additional 3 subjects per experiment (n=3) will be included for piloting.

4.6 Vulnerable Populations:

All subjects must be able to provide their own consent. This study is above minimal risk and we do not want to enroll participants who do not understand the risk/benefit ratio of the study, particularly when there is no benefit to the participants. For this reason we exclude people with IQ lower than 80. We exclude and rule out pregnant women because of the unknown effects of the shocks and of the fMRI on the developing fetus. We exclude non-English speakers since not all the instruments and test we use are translated and validated in Spanish or other languages. Based on our experience, we made the decision that 50 would be the upper age limit to prevent age-related changes in brain structure and function from confounding our analyses. Patients will not be taken off medications for the purpose of the study.

CONFIDENTIAL

5 Study Procedures

Does your study use MRI? (CAMRIS is the appropriate contact for all studies involving MRIs)

Yes No

Check of all that apply:

1.5T MRI
 3T MRI
 7TMRI

Does the MRI use investigational sequences and/or coils?
(See Experimental Device Clause)

Yes No Unsure (if unsure you need to contact CAMRIS)

Experimental Device Clause -- Some of the pulse sequences and/or RF coils are not FDA approved but are considered to pose no more than minimal risk.

Does your study include pregnant women?
(See Pregnancy Clause and Justification)

Yes No

Pregnancy Clause -- Although there are no known risks related to MRI on pregnant women or a fetus, there is a possibility of yet undiscovered pregnancy related risks. Since there is no possible benefit from participating in this protocol for a pregnant woman, we will exclude pregnant women.

Does the MRI require the use of Contrast Agents?
(See Contrast Risks)

Yes No

Does your study involve the exposure to radiation, radiotracers and/or radiological imaging modalities?

Yes No (If No, no RRSC review is needed)

Will any of the radiation exposure result from procedures that are or could be performed solely as a result of a subject's participation in the research protocol?

Yes No

CONFIDENTIAL

Ultrasound

Yes

No

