6.2 Sample Size and Power Determination

Because we have several outcome measures, and because there is little known about how TMS will affect these outcome measures, we are conducting a single power analysis to determine sample size, based on a moderate effect size of ($f=0.5$). If we set power at 0.8 and use a corrected two-tailed alpha of 0.025 we would need 26 subjects per group to detect a main effect. Assuming a 15% unusable data rate and 3 pilot subjects, we will need 63 total subjects. However, this will be updated prior to enrollment based on the best available information at the time. To ensure that we are adequately powered across the study arms, and to account for additional dropout due to scheduling issues, we plan to recruit up to 75 participants.

7 Safety and Adverse Events

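### The 3-level stimulation main effect mixes TBS with visit order, because pre-stimulation is always Week 1; Section 6.1 should tie Aims 1 and 2 to the sham-based tests, and Section 6.2 should name the effect it powers

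*Combined protocol and SAP*

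**What the plan says.** Section 6.1 gives the same analysis for Aims 1 and 2: "The main analysis will be a 3 [stimulation: pre-stimulation vs. post-active vs. post-sham] by 2 [protocol: cTBS vs. iTBS] repeated-measures ANOVA". It names no main effect, interaction or contrast as the test of either aim. Counterbalance order appears only among covariates that may be used. For Aim 3, by contrast, the section does specify a paired comparison of active with sham.

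Section 3.1 fixes the timing. In Week 1, "subjects will undergo a pre-stimulation behavioral visit where they complete the NPU threat task and the Sternberg WM paradigm". The two post-stimulation tests fall on the fifth visit of Weeks 2 and 4. Protocol (cTBS or iTBS) is randomised between subjects, and "the order of stimulation (active vs. sham) will be counterbalanced across subjects". The pre-stimulation visit has no part in that counterbalancing.

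The hypotheses are framed against sham. For Aim 1, Section 2 (repeated in 3.2) says "we expect excitatory but not inhibitory TBS (compared to sham) to reduce induced anxiety". For Aim 2, Section 3.2 expects iTBS, compared with sham, to improve Sternberg accuracy under threat; Section 2 states the same expectation for 10 Hz rTMS.

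Section 6.2 assumes f = 0.5, power 0.8 and a corrected two-tailed alpha of 0.025, and concludes that "we would need 26 subjects per group to detect a main effect". It does not say which main effect. It adds that the figure will be updated before enrollment. Section 4.5 says: "The target number of completers will be N=56".

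**The concern.** Pre-stimulation is both a level of the stimulation factor and the first visit, for everyone. If scores change between Week 1 and the later tests for reasons unrelated to TBS, the change enters the stimulation main effect directly. An order covariate cannot remove it, because pre-stimulation comes first under either order.

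Aim 2 is the more exposed. Its outcome is percent correct, and subjects practise the task before the first post-stimulation test: at Lab Visit 1, at the MRI visit ("Next subjects will undergo a two runs of the Sternberg task, without shocks, probes, or TMS pulses to serve as functional localizers"), and in the stimulation week ("The first 4 visits will be stimulation visits where they receive either active or sham stimulation while doing the Sternberg WM task"). Aim 1 is better protected, because FPS and APS are within-visit difference scores and habituation and the shock workup are repeated at each test visit.

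One stated effect of the main analysis, possibly the one the sample size refers to, can thus be significant with no TBS effect. Neither main effect matches the hypotheses. The protocol main effect averages over active, sham and pre-stimulation. The stimulation main effect averages over two protocols that are expected to act differently. For Aim 2 the 3 by 2 layout also has no threat/safe term, although each Sternberg run contains both block types and the expectation concerns threat.

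**Working it through.** **The plan's own figure.** Inputs from Section 6.2: f = 0.5, power 0.8, two-sided alpha 0.025.

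- Three-level within-subject effect in one group, df 2 and 2(n−1), noncentrality f² × error df. At n = 26 this is 0.25 × 50 = 12.5 and power is 0.804; at n = 25 power is 0.784. Result: 26.
- Fixed-effects F with 2 df and six cells: N = 51 in total (power 0.809; 0.799 at N = 50), so 26 per group after rounding up.
- Two-level protocol main effect, where f = 0.5 is a standardised difference of 1.0: 21 per group (power 0.815), or 20 by the normal approximation.

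So 26 fits a 2-df effect better than the protocol main effect. The formula is not stated, and the second calculation would be the same for the interaction. The total of 63 follows from 52 × 1.15 + 3 = 62.8. The ceiling of 75 follows from Section 4.5 instead: 56 + 11 + 5 + 3 = 75. That section implies 56/2 = 28 completers per group, not 26.

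**Stimulation main effect with no TBS effect.** Assumptions: unit SD, equal correlation ρ between visits, and a shift s from Week 1 common to both post tests and both groups. The level deviations are −2s/3, s/3 and s/3, with sum of squares 2s²/3. With N subjects, noncentrality is N × (2s²/3)/(1−ρ), on 2 and 2(N−2) df. For N = 52, ρ = 0.5 and s = 0.3: 52 × 0.06/0.5 = 6.24, and the rejection rate is 47%.

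| Shift (SD) | N = 52, ρ = 0.5 | N = 52, ρ = 0.7 | N = 56, ρ = 0.5 | N = 56, ρ = 0.7 |
|---|---|---|---|---|
| 0.1 | 6% | 9% | 6% | 9% |
| 0.2 | 20% | 35% | 22% | 38% |
| 0.3 | 47% | 73% | 51% | 77% |
| 0.5 | 94% | >99% | 95% | >99% |

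Nominal is 2.5%. Simulating the mixed ANOVA at 26 per group and ρ = 0.5 agrees: 20%, 48% and 94% at shifts of 0.2, 0.3 and 0.5 SD. In the same runs the stimulation by protocol interaction and the active versus sham contrasts reject in 2.3–2.7%.

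The main effect can also miss a real effect. With opposite iTBS and cTBS effects of 0.5 SD and no shift, it is significant in 2.5% of simulated trials, against 94% for the 2-df interaction.

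**Power of the sham-based tests, 26 per group, two-sided alpha 0.025.** Let d be the active-minus-sham difference divided by its own SD, √(2(1−ρ)) outcome SDs. This equals one outcome SD at ρ = 0.5. For the protocol contrast, d is the difference between protocols in that quantity. Noncentrality is d√(26/2) for the contrast (50 df) and d√26 within iTBS (25 df).

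| d | Protocol × (active − sham) | Active vs sham within iTBS |
|---|---|---|
| 0.5 | 31% | 57% |
| 0.7 | 59% | 87% |
| 1.0 | 90% | 99.5% |

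The smallest d with 80% power is 0.88 for the contrast and 0.64 within iTBS. A d of 1.0 is one reading of f = 0.5; the documents do not give the mapping.

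**The case against.** The strongest reply is that the planned ANOVA already contains valid tests. Active versus sham is counterbalanced and protocol is randomised, so a shift common to both groups leaves the interaction and the sham contrasts at their level. The hypotheses in Sections 2 and 3.2 are stated against sham, so a pre versus post change would not satisfy them. This stands. A reader might infer that the whole 3 by 2 analysis is invalid, or that pre-stimulation must be removed from it; neither follows. What remains is that Section 6.1 does not carry the sham comparison into the analysis, so the deciding test stays open until the data are seen.

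Second, a reader might infer from the 31% and 57% figures that the trial is underpowered. The documents do not support that: those figures rest on an assumed d of 0.5. If f = 0.5 is read as d = 1.0, power is 90% and 99.5%. Section 6.2 also uses an alpha described as corrected, in a paragraph that opens with the number of outcomes, and promises an update before enrollment. The gap is that the stated power is not tied to the comparison each aim is about.

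Third, no document gives a visit shift, so the higher rejection rates are illustrations and bear less on Aim 1. That is fair.

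Fourth, for Aim 2 one could insist on threat accuracy within iTBS, as Section 3.2 expects. But Section 6.1 words the aim as anxiety-related deficits and as continuous versus intermittent, which favours threat-minus-safe accuracy and the protocol contrast. The documents do not settle this.

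**Conclusion.** The concern holds for the 3-level stimulation main effect and for any pre versus post contrast, and mainly for Aim 2 accuracy. At 26 per group, the false-positive rate of that main effect rises from 2.5% to between 6% and over 99% for assumed shifts of 0.1 to 0.5 SD and correlations of 0.5 to 0.7. This rests on a shift common to both groups, equal correlations between visits and balanced order.

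It is tempting to conclude from the match with 26 per group that the trial was sized on the confounded effect. The match is suggestive only, since the formula is not given and other 2-df calculations reach the same number.

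This should be fixed before unblinding. It is a defect of specification, not of design: the data will support valid sham-based tests, and the plan has to name them.

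**What to change.** 1. In Section 6.1, name protocol × (post-active minus post-sham), followed by post-active versus post-sham within iTBS, as the test of Aim 1. Name post-active versus post-sham under iTBS as the test of the Aim 2 expectation in Section 3.2. State that the 3-level main effect and pre versus post differences are not evidence of a TBS effect. Pre-stimulation may stay in the model, or serve as a baseline or descriptively.
2. For Aim 2, include the threat/safe condition, and fix before unblinding whether threat accuracy or threat-minus-safe accuracy is decisive. Reconcile 10 Hz rTMS in Section 2 with iTBS in Section 3.2.
3. Make period/order (Week 2 versus Week 4) a fixed term. With balanced order this protects power, not validity; for a 0.7 SD effect it gains about 2 points or less at period shifts up to 0.2 SD.
4. In Section 6.2, name the effect that 26 per group refers to, say what the corrected 0.025 corrects for, reconcile 26 per group with the 56 completers in Section 4.5, and give power for the named tests over a range of effects.

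Cost: no new data, only SAP wording and one degree of freedom for period. For a 0.7 SD iTBS-only effect at 26 per group, the Aim 1 contrast has about 4–5 points less power than the 2-df interaction (59% against 63% at correlation 0.5).
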